### 5.2 Secondary objectives and endpoints

*Secondary objective 1:*

- To compare dose regimens of VRC07-523LS delivery for their ability to sustain mucosal mAb levels at serial timepoints post repeat administration

*Secondary endpoint 1:*

- Levels of VRC07-523LS in genital and rectal secretions and tissue at specified timepoints

*Secondary objectives 2:*

- To determine whether ADA can be detected in serum

*Secondary endpoint 2:*

- Serum concentration of ADA in each group measured at multiple timepoints from baseline through the final study visit

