**Table 9-1 HVTN 128 Sampling and product administration schedule**

	D –14 W –2	D0 W0	D14 W2	D112 W16	D126 W18	D224 W32	D238 W34	D336 W48
Product Administration		X		X		X		
Blood collection	X	X	X	X*	X	X*	X	X
Rectal, cervicovaginal and seminal secretion collection	X		X	X*	X	X*	X	X
Cervical, rectal, and vaginal biopsy collection	X		X				X	X

\* Specimen collections to be done prior to the infusion

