## Appendix E Laboratory procedures

Procedure	Ship to 	Assay location 	Tube Type 	Tube size (vol. capacity) 	Visit:	1	2	3	4	5	6	7	8	9	10 	Total
					Day:	Screening visit 	D-14	D0	D14	D112	D126	D224	D238	D336	D350	
					Week:	W-2	W0	W2	W16	W18	W32	W34	W48	W50		
							Inf #1		Inf #2		Inf #3					
BLOOD COLLECTION																
Screening/Diagnostic																
Screening HIV test	Local lab	Local lab	SST	5mL	5	—	—	—	—	—	—	—	—	—	—	5
HBsAg/anti-HCV	Local lab	Local lab	SST	5mL	5	—	—	—	—	—	—	—	—	—	—	5
HIV diagnostics 	UW-VSL	UW-VSL	EDTA	10mL	—	—	—	—	10	—	10	—	20	—	—	40
Safety Labs																
CBC/ Diff / Platelets 	Local lab	Local lab	EDTA	5mL	5	—	—	5	—	5	—	5	—	—	—	20
Chemistry panel 	Local lab	Local lab	SST	5mL	5	—	—	5	—	5	—	5	—	—	—	20
Hormone Levels																
Hormone panel 	Local lab	Local lab	SST	8.5mL	—	8.5	—	8.5	8.5	8.5	8.5	8.5	8.5	8.5	—	59.5
STI Serology																
Syphilis 	Local lab	Local lab	SST	5mL	5	—	—	—	—	—	—	—	—	—	—	5
Drug Levels/Detection																
VRC07-523LS Ab levels	CSR	HVTN Labs / VITL	SST	8.5mL	—	y	—	y	y	y	y	y	y	y	—	0
Anti-Drug Antibody (ADA)																
ADA detection assays	CSR	HVTN Labs / VITL	SST	8.5mL	—	y	—	—	y	—	y	—	y	—	—	0
ADA functional neutralization	CSR	HVTN Labs	SST	8.5mL	—	y	—	—	y	—	y	—	y	—	—	0
mAb Reaction Labs																
Trypsase / C3 and C4 complement / Cytokines	CSR	ARUP	SST	8.5mL	—	—	See footnote 17								—	0
ADA detection assays	CSR	HVTN Labs / VITL	SST	8.5mL	—	—	See footnote y								—	0
ADA functional neutralization	CSR	HVTN Labs	SST	8.5mL	—	—	See footnote y								—	0
STORAGE																
Serum storage	CSR	—	SST	8.5mL	—	76.5	17	51	51	51	51	51	51	51	—	399.5
Visit total					25	95	17	79.5	69.5	69.5	69.5	79.5	89.5	89.5	0	594
56-Day total					25	120	137	216.5	69.5	139	69.5	149	89.5	89.5		
URINE COLLECTION																
Urine dipstick 	Local lab	Local lab			X	—	—	X	—	X	—	X	—	—	—	
Pregnancy Test 	Local lab	Local lab			X	X	X	X	X	X	X	X	X	X	—	
Chlamydia/Gonorrhea 	Local lab	Local lab			X	—	—	X	—	—	—	X	X	—		
RECTAL SWAB COLLECTION																

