A bridging assay to detect ADA against a biologic drug product begins with covalently conjugating drug product with either biotin or the Sulfo-Tag label. Biotinylated and Sulfo-Tagged mAb are then combined and mixed with serum that may contain ADA. When an ADA response is present, complexes comprised of the ADA and one or both types of labeled mAb species can form. In some cases, because antibodies are multivalent, the ADA will act as a bridge between the biotinylated and Sulfo-Tagged drug in a ternary complex. Following an incubation to allow complex formation, this mixture is added to a proprietary streptavidin-functionalized plate, washed, and the presence of ADA responses, as indicated by the presence of ternary or “bridged” complexes, is detected. The Meso Scale Diagnostics (MSD™) instrument passes an electrical current through the plate, exciting any Sulfo-Tag within proximity of the plate surface, and resulting in electrochemiluminescence, which is expressed in relative light units (RLU). During assay qualification, a positivity cut point is established and utilized to determine whether a sample is ADA Screening Assay positive based on its RLU signal intensity. While only complexes containing both biotinylated and Sulfo-Tagged drug will result in signal, additional complexes are likely to form that are nonconductive to signal measurement (e.g. biotin:biotin or Sulfo-Tag: Sulfo-Tag bridged products). Formation of these nonproductive complexes has been taken into consideration during the development phase, and efforts have been made to maximize sensitivity by reducing the likelihood of formation of these nonproductive complexes. The criteria for establishing positivity cut points in the Tier I assay are designed to minimize the risk of false negatives. As such, a certain proportion of ADA-negative subjects will be classified as positive in

this screening assay but can later be investigated with Tier II confirmatory and, in some cases, Tier III characterization assays. The assays are all performed in 96well plates for high throughput capacity. The screening assay has been qualified, and the specificity and titering assays have been deemed fit for purpose.

All designated serum samples will be assayed at a 1:12 dilution of serum for Tiers I and II. In Tier III, titers will be defined as lowest fold dilution from a starting dilution of 1:12 at which the test sample remains above the assay cut point.

Screening assay

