- i. If the average value of a test sample exceeds the assay cut point, that sample is classified as Tier I positive.
- ii. %CVs are calculated by the Discovery Workbench Software. If any control exceeds an average CV of 20%, an investigation of the run will be required. If any sample exceeds a CV of 20%, that sample will need to be rerun.

Confirmation assay

- i. Tier 1 positive samples are retested in the presence of free drug. If free drug reduces signal by more than the specificity threshold, these samples are considered Tier II confirmed.

Titering assay

- i. Test samples that are Tier II confirmed will be titrated using the screening assay across a dilution series. The lowest fold dilution at which the test sample remains above the assay cut point is considered its titer.

The following evaluation criteria will be employed for screening, confirmatory and tittering assays:

- i. %CVs must be below 20% for sample replicates
- ii. Positive controls must exceed values established during qualification

ADAs will be categorized as treatment induced, boosted, or independent based on the longitudinal profile observed, with boosted responses defined by a 3-fold increase in titer from baseline. Any sample that was either Tier I or Tier II negative at baseline, then Tier II positive at a later timepoint is considered as induced ADA. Only samples that were ADA positive at baseline have their titers compared to follow up timepoints to determine if a response is boosted or independent.

The statistical analysis tabulates frequencies of serum samples in which ADA were detected, along with their 95% confidence intervals, by treatment group, timepoint, and ADA assay tier. The analysis will also report summary statistics (e.g., mean, median, range, as appropriate) of ADA levels among samples with detectable ADA levels.

If ADA is detected in more than one sample, the percentages of participants with detectable ADA levels, along with their 95% confidence intervals, will also be plotted as a function of time by treatment group.

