		Rectal	2,4,5,6,7,8,9	168

24	Biopsy	Colorectal	2,4,8,9	96
		Cervical	2,4,8,9	96
		Vaginal	2,4,8,9	96

Statistical endpoints

To account for heterogeneity in size of biopsies and absolute concentration (e.g., rectal secretions flushed with media during collection) of the samples, IgG- and protein-normalizations for mucosal samples are performed by dividing VRC07-523LS levels (pg/mL) by the total IgG (ng/mL) and protein concentrations (mg/mL), respectively, as following:

- VRC07-523-LS concentration normalized by total IgG (pg VRC07-523LS/ng total IgG):
 - Units: VRC07-523LS units are pg/mL, and total antibody units are ng/mL. Truncate as specified in the Truncation Rule section below.
 - Antibody normalized concentration = truncated observed concentration / truncated total antibody
- VRC07-523-LS concentration normalized by total protein (pg VRC07-523LS/ng total protein):
 - Units: VRC07-523LS units are pg/mL, and total protein units are mg/mL (milligrams per milliliter). To convert mg to ng, first truncate as specified in the truncation rule section below, then multiply total protein by 1×10^6 (1,000,000).
 - Protein normalized concentration = truncated observed concentration / (10^6 x truncated total protein)

IgG-normalizations for serum samples are performed by dividing VRC07-523LS levels (μ g/mL) by the average reference values for total IgG concentrations in serum in the USA (1165 mg/dL), as following:

- VRC07-523-LS concentration in serum normalized by total IgG (pg VRC07-523LS/ng total IgG):
 - Units: VRC07-523LS units are μ g/mL, and total antibody units are mg/dL. Truncate as specified in the Truncation Rule section below, then divided total antibody by 100.
 - Antibody normalized concentration = truncated observed concentration / (10^{-2} x U.S. reference total antibody)

Truncation rules are applied for SMCxPro, serum, total IgG, and total protein data as following:

- SMCxPro truncation: For results under the smaller value of limit of detection (LLoD) and sample type specific limit of quantification (LLoQ), they are truncated at lower limit of quantification (LLoX) / 2 where LLoX is minimum(LLoQ, LLoD)
- serum truncation: Baseline serum concentrations below the lower limit of quantification (LLoQ = 45.7 ng/ml = 0.0457μ g/ml) are replaced with LLoQ/2. No post-baseline concentrations are below the LLoQ.

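### SAP 8.2 reads ADA results without regard to concurrent drug level, although drug is quantifiable at every post-baseline ADA visit; ADA rates may be underestimated, by an unknown and possibly zero amount

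*SAP*

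**What the plan says.** Secondary objective 2 (Protocol 5.2) is: "To determine whether ADA can be detected in serum".

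**Timing.** Protocol Appendix E schedules the "ADA detection assays" at visits 2, 5, 7 and 9 (days −14, 112, 224 and 336). For weeks 16 and 32, Table 9-1 carries the footnote "Specimen collections to be done prior to the infusion". Week 48 is 16 weeks after the last infusion, and no later serum sample is planned. Drug levels are scheduled at the same four visits from the same stored serum (Appendix E, footnote y).

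**Assay.** SAP 8.2 describes a bridging assay in tiers. A screening signal arises when ADA link biotin-labelled drug to Sulfo-Tag-labelled drug. "All designated serum samples will be assayed at a 1:12 dilution of serum for Tiers I and II". Screen-positive samples are retested with unlabelled drug added: "If free drug reduces signal by more than the specificity threshold, these samples are considered Tier II confirmed". Only confirmed samples are titrated. ADA count as induced if absent at baseline and Tier II positive later, and as boosted if the titre of a baseline-positive participant rises 3-fold.

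**Analysis.** "The statistical analysis tabulates frequencies of serum samples in which ADA were detected, along with their 95% confidence intervals, by treatment group, timepoint", and also by tier. SAP 8.2.1 specifies Wilson intervals.

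**Drug level.** The truncation rules in SAP 8.3 give the serum limit ("LLoQ = 45.7 ng/ml") and add: "No post-baseline concentrations are below the LLoQ".

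**The concern.** The confirmatory tier and the sampling schedule bear on each other, but SAP 8.2 does not connect them. If added free drug lowers the bridging signal, drug already in the participant's serum is the same competitor. A post-dose sample containing ADA could then fall below the screening cut point. With no third category, it would enter the response rate as not detected. It would not be looked at again, because confirmation, titration and the functional assay (Protocol 10.5) each act only on samples positive at the step before.

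Baseline is drug-free and follow-up is not. The induced and boosted classifications therefore compare a sample without the competitor to one with it, and any error runs towards missing ADA. The doses differ 3-fold, so a lower ADA rate at 30 mg/kg could reflect drug in the tube rather than less immunogenicity.

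**Working it through.** **1. Samples affected.** Post-baseline ADA visits are 5, 7 and 9, so 24 × 3 = 72 samples are planned. Protocol 6.1 takes 17% as a reasonable missing-data rate, which would leave about 72 × 0.83 ≈ 60. Each measured one falls at a visit where the SAP reports drug at or above 45.7 ng/mL. At the 1:12 dilution, that limit corresponds to 45.7/12 = 3.8 ng/mL contributed by the sample.

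**2. The plan's own interval.** For 0/n the Wilson upper bound is z²/(n + z²), with z² = 3.84. For n = 12 this is 3.84/15.84 = 24.2%; for n = 24 it is 3.84/27.84 = 13.8%. Both match Protocol 6.1.1. These intervals describe sampling error only. They contain no term for lost sensitivity.

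**3. Can the drug level settle the matter?** The SAP gives no trough values. As an illustration, take one compartment and one dose, C = dose × 1000/V × 2^(−112/t½), with assumed V of 40–80 mL/kg and assumed half-life of 10–60 days:

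- 10 mg/kg, lowest: 10,000/80 × 2^(−11.2) = 0.053 mcg/mL
- 10 mg/kg, highest: 10,000/40 × 2^(−1.87) = 68.6 mcg/mL
- 30 mg/kg, under dose proportionality: three times these, 0.16 to 206 mcg/mL

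After 1:12 dilution the 10 mg/kg range is about 0.004 to 5.7 mcg/mL and the 30 mg/kg range about 0.013 to 17 mcg/mL. Each spans some 1,300-fold, too wide to say whether an unstated tolerance is exceeded.

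**4. What masking would do if it occurred.** Apparent rate = true rate × sensitivity under drug; P(0/12) = (1 − apparent rate)^12. The sensitivities are assumptions. With a true rate of 25% and n = 12:

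| Sensitivity | Apparent rate | P(0/12) | Wilson 95% coverage of true rate |
|---|---|---|---|
| 1.0 | 25% | 0.03 | 91% |
| 0.7 | 17.5% | 0.10 | 89% |
| 0.5 | 12.5% | 0.20 | 80% |
| 0.3 | 7.5% | 0.39 | 61% |

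At a true rate of 10% coverage does not suffer (97% at sensitivity 1.0, above 99% at 0.5), because the interval is already wide. P(0/12) still rises from 0.28 to 0.54.

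**5. Arm contrast.** With equal true rates of 25% and assumed sensitivities of 0.8 at 10 mg/kg and 0.5 at 30 mg/kg, the spurious difference is 25% × (0.5 − 0.8) = −7.5 points. With full sensitivity in both arms it is zero.

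**The case against.** The strongest reply is that masking is possible but not shown. Much of that stands.

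- A reader might infer that ADA rates **are** biased down, and more so at 30 mg/kg. The documents do not support this. If the assay tolerates trough drug in both arms, the bias and its dose gradient are both nil.
- A reader might infer that the SAP itself says free drug suppresses screening. It says so only of drug deliberately added in Tier II. Extending this to residual drug follows from the assay's mechanism, but it is inference.
- Quantifiable is not the same as interfering. The 45.7 ng/mL limit belongs to the concentration assay and says nothing about ADA tolerance.
- The schedule helps. No ADA sample is scheduled at the 2-week post-dose visits; every post-baseline one is at trough, and dilution lowers the drug further.
- The screening assay is described as qualified. Its qualification data are not in these documents, so it cannot be claimed that tolerance was never studied.
- No between-arm ADA test is planned; the output is descriptive.

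What does not stand is that existing safeguards cover the point. The only interference SAP 8.2 discusses is same-label complexes, a different mechanism. A cut point set to limit false negatives does not show performance with drug present, and the replicate and control criteria do not address drug in the test sample. Rates are still tabulated by arm, where readers will compare them.

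**Conclusion.** The point holds as a limit on interpretation, not as a demonstrated bias. Drug is quantifiable at every post-baseline ADA visit, the confirmatory tier relies on free drug lowering the signal, and a sample below the cut point has only one reading whatever its drug level. ADA rates and the induced and boosted classifications may therefore be underestimated, possibly more at 30 mg/kg.

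The size is unknown and could be zero. The direction rests on residual drug competing as added drug does, and the dose gradient on higher trough drug at 30 mg/kg. The sensitivity figures show only scale: at a true rate of 25%, halving sensitivity takes P(0/12) from 0.03 to 0.20. As planned, the analysis cannot tell a true negative from a masked one, although the paired concentrations that would help are already being measured.

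**What to change.** In SAP 8.2:

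1. Merge each ADA result with the same-visit serum concentration.
2. State the drug-tolerance level from assay qualification. Report samples below the cut point and above tolerance as 'not detected, inconclusive', by arm and visit.
3. Keep the current all-sample rate, labelled as a lower bound with respect to masking.
4. Beside it, show the rate among samples at or below tolerance, applying the limit to positives and negatives alike.
5. If no tolerance level exists, tabulate ADA status against concurrent concentration and word null results as 'not detected in the presence of drug'.
6. Do not interpret a between-arm ADA difference without this table.

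Step 4 must not remove negatives only. Suppose 3 of 12 samples are positive and 6 of the 9 negatives exceed tolerance. Dropping just those six turns 3/12 = 25% into 3/6 = 50%. If positives exceed tolerance in the same two-thirds proportion, the symmetric rule leaves 1 positive and 3 negatives: 1/4 = 25%. The restricted rate still assumes that ADA status is unrelated to drug level. If ADA speed clearance it will run high, which is a reason to show both rates.

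The cost is SAP wording and one merged table, with no new participant samples. SAP section 1 already foresees an update before further immunogenicity analyses. The downside is that fewer samples can be called negative and the restricted intervals widen. With 4 evaluable samples and none positive, the Wilson upper bound is 3.84/7.84 = 49.0%, against 24.2% for 0/12. If no sample is at or below tolerance, the restricted rate cannot be estimated.

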8.2.1 List of Tables

- Response rate and corresponding 95% confidence intervals using the Wilson score method by tier, visit and treatment arm.

- List of participants with Tier II confirmed positive responses.

8.2.2 List of Graphs

- Line plots of ADA Tier II confirmed response by treatment arm.
- Line plots of ADA Tier III titering responses for participants with Tier II confirmatory response.

8.3 PK-Single Molecule Counting (PK-SMC)

SMCxPro for VRC07-523LS concentrations in mucosal tissues and secretions

Pharmacokinetic - Single Molecule Counting (PK-SMC) assay will be used to measure passively infused VRC07-523LS broadly neutralizing monoclonal antibody in HVTN 128 participant mucosa (secretions and biopsies) using 5C9 anti-idiotype antibody (anti-ID).

This assay will address the testing necessary to satisfy applicable primary, secondary, and exploratory objectives & endpoints as described in the HVTN 128 Protocol.

i. Primary Objectives 2:

- To determine whether multiple infusions of VRC07-523LS reach and maintain detectable levels in the mucosa
- To correlate levels of VRC07-523LS in serum and the mucosa

ii. Primary Endpoints 2:

- Levels of VRC07-523LS in genital and rectal secretions, as well as cervical, vaginal, and rectal tissues at the collection timepoints
- Levels of VRC07-523LS in serum out to Week 48, 16 weeks after the last product administration

iii. Secondary Objective 1:

- To compare dose regimens of VRC07-523LS delivery for their ability to sustain mucosal mAb levels at serial timepoints post repeat administration

iv. Secondary Endpoint 1:

- Levels of VRC07-523LS in genital and rectal secretions and tissue at specified timepoints

v. Exploratory Objective 2:

- To develop predictive mucosal population pharmacokinetic models of VRC07-523LS administered IV

The SMCxPro assay is a highly sensitive sandwich-based immunoassay that uses a magnetic bead system akin to flow cytometry to detect very low concentrations (theoretically down to single molecules) of biomarkers such as monoclonal antibodies. It is the successor to the Singulex instrument system and operates on similar principles, but the instrument software and thus expected output format are significantly different from Singulex. In HVTN studies, this assay is typically used to assess the mucosal concentrations of administered monoclonal antibodies, as part of PK (pharmacokinetic) analyses. The ultra-sensitive capabilities of the SMCxPro instrument enables a high degree of sensitivity that allows for the analysis of proteins down to femtogram/mL levels. VRC07-523LS levels are normalized relative to total protein and/or total IgG concentrations. Hemoglobin measurements are used to perform quality control of mucosal secretions.

Using the proprietary SMC Capture Antibody Labeling Kit, anti-idiotype (anti-ID) antibody is labeled and then coated onto magnetic microparticle beads. Anti-human Fc secondary detection antibody of the appropriate isotype (ex: anti-human IgG1 Fc) is labeled with a fluorophore using the SMC Detection Antibody Labeling Kit. Labeled and coated microparticle beads are mixed separately with samples, standards, and controls and incubated to allow antibody capture. Captured monoclonal antibodies are detected using the labeled secondary detection antibody. This forms a sandwich complex with the target analyte between the magnetic bead anti-ID antibody and the labeled secondary detection antibody, comparable to a sandwich ELISA.

The magnetic properties of the microparticle beads are used to hold the beads in place for washing steps. After several rounds of washing to remove excess unbound reagents, the complexes are broken apart by the addition of an acidic elution buffer and the released detection molecules, which are now proportional in quantity to the analyte, are quantified by fluorescence detection using the SMCxPro instrument. The method is derived from the Singulex three-curve weighting system, but without the ability to export the separate curves and their weights for each assay point.

Study samples and controls are run in triplicate. Where possible, all of a participant's samples of a given specimen type are included in the same assay batch, in order to minimize batch effects on PK trajectories. Standard curves containing known concentrations of the target analyte in human mucosal test samples will be run on each plate to establish quantification criteria. These standard curves are fit to a 5-PL logistic regression to convert response readouts of samples to a derived mAb concentration. Triplicate wells containing HIV-seronegative human reference serum and negative control beads are also run in each assay batch as a negative control to ensure specificity of binding. Sample data is released only where both preset criteria are met: 1) Five consecutive standard curve points recover 70-130% of expected concentration. 2) Three consecutive spiked positive controls recover 70-130% of the expected concentration. Linear ranges vary by specific analyte and are available with standard curve data for each dataset. Results are reported in pg/mL.

PK-Binding Antibody Multiplex Assay (PK-BAMA) for VRC07-523LS concentration in serum

Pharmacokinetic-Binding Antibody Multiplex Assay (PK-BAMA) will be used to measure levels of passively infused VRC07-523LS broadly neutralizing monoclonal antibody in HVTN 128 participant sera using 5C9 anti-idiotype antibody (anti-ID).

One of the primary objectives of this study is to determine VRC07-523LS drug levels using the anti-idiotype PK-BAMA in serum collected at the designated timepoints.

Carboxylated magnetic beads (Magplex, Luminex) are covalently coupled to NeutrAvidin and are then subsequently bound to a biotinylated goat anti-mouse IgG Fc antibody. This is then followed by binding of the 5C9 anti-idiotype monoclonal. Through this process, 5C9 will be oriented to freely bind to the paratope of the VRC07-523LS. Sample is then added to the coated beads and incubated for 120-125 minutes in a plate shaker. At the end of the incubation, plates are washed using BAMA wash buffer. Bound VRC07-523LS are detected using a goat anti-human IgG Fc, multi-species serum protein (SP), conjugated to phycoerythrin (PE). Microspheres are read on a Bioplex 200 instrument to measure Fluorescence Intensity (FI). Mean Fluorescence Intensity (MFI) values are used to quantify VRC07-523LS that has been bound to 5C9 anti-idiotype antibody in solution.

VRC07-523LS IgG standard curves are run on each plate to quantify VRC07-523LS IgG in human mucosal test samples. Standard curves are fit to a 5-PL logistic regression to convert response readouts of samples to VRC07-523LS IgG mAb concentration. Duplicate wells containing HIV-1 seronegative normal human reference serum and negative control beads are also run in each assay to ensure specificity of binding.

ELISA for Hemoglobin (Hb) and protein concentration

The purposes of the hemoglobin (Hb) quantitation assays are to measure blood contamination in mucosal secretions. Oricol devices permit the collection of rectal secretions from the rectum, and vaginal secretions will be collected via Softcup collection. Integral to the detection of VRC07-523LS in secretions is the need to demonstrate that collections are free of contaminating blood, where the antibody is found at high concentrations. This study aims to provide early feedback to the sites regarding the levels of Hb in rectal secretions from multiple clinicians, to ensure the sample is optimal for the measurements of the primary endpoint.

Preliminary Results are determined using the ELISA Plate Reader (Molecular Devices) SpectraMax i3X absorbance (Hemoglobin) and fluorescence (protein concentration). Assays are assessed for QC using the standards ran on each plate.

The Quant-iT™ Protein Assay Kit (Invitrogen™) is used to measure the total protein in samples provided by study participants. The kit provides concentrated assay reagent, dilution buffer, and pre-diluted BSA standards. Simply dilute the reagent, load it into the wells of a microplate, add 1-20 µL of sample, mix, then measure the fluorescence. The assay is highly selective for protein and exhibits very little protein-to-protein variation. The assay is performed at room temperature, and the signal is stable for 3 hours. Common contaminants, such as salts, solvents, or DNA—but not detergents—are well tolerated in the assay.

Bio-Plex Pro™ Human Isotyping Assay for IgG concentration

The Bio-Plex Pro™ Human Isotyping Assay (Bio-Rad Laboratories, Inc.) is used to measure IgG in mucosal samples provided by study participants. The kit provides magnetic beads, detection antibodies, standards, controls, and reagents for detecting human IgG1, IgG2, IgG3, IgG4, IgA, and IgM. Samples are diluted in the provided kit buffer and mixed with the multiplex magnetic bead panel in a 96-well plate. Plates are washed with the kit-provided wash buffer, and secondary detection antibodies are added per the package insert instructions. Plates are read on a BioPlex 200 instrument to measure Fluorescence Intensity (FI). Mean Fluorescence Intensity (MFI) values are used to quantify isotype concentrations. Sample isotype concentrations are derived from the kit-supplied standard curve.

Specimens

A total of 24 participants and 504 secretion (semen, cervicovaginal, and rectal) samples (168 of each specimen type) will be tested at 7 timepoints (visits 2, 4, 5, 6, 7, 8 and 9) from Groups 1 and 2. A total of 24 participants and 168 serum samples will be also tested at 7 timepoints (visits 2, 4, 5, 6, 7, 8 and 9) from Groups 1 and 2. A total of 24 participants and 288 biopsy (colorectal, cervical and vaginal) samples (96 of each specimen type) will be tested at 4 timepoints (visits 2, 4, 8 and 9) from Groups 1 and 2.

Summary of sample numbers and specimen types proposed for testing is summarized in the table below:

No. of Participants	Specimen Type		Timepoint (visit)	Total no. of samples
24	Secretion	Semen	2,4,5,6,7,8,9	168
		Cervicovaginal	2,4,5,6,7,8,9	168
		Rectal	2,4,5,6,7,8,9	168

24	Biopsy	Colorectal	2,4,8,9	96
		Cervical	2,4,8,9	96
		Vaginal	2,4,8,9	96

Statistical endpoints

To account for heterogeneity in size of biopsies and absolute concentration (e.g., rectal secretions flushed with media during collection) of the samples, IgG- and protein-normalizations for mucosal samples are performed by dividing VRC07-523LS levels (pg/mL) by the total IgG (ng/mL) and protein concentrations (mg/mL), respectively, as following:

- VRC07-523-LS concentration normalized by total IgG (pg VRC07-523LS/ng total IgG):
 - Units: VRC07-523LS units are pg/mL, and total antibody units are ng/mL. Truncate as specified in the Truncation Rule section below.
 - Antibody normalized concentration = truncated observed concentration / truncated total antibody
- VRC07-523-LS concentration normalized by total protein (pg VRC07-523LS/ng total protein):
 - Units: VRC07-523LS units are pg/mL, and total protein units are mg/mL (milligrams per milliliter). To convert mg to ng, first truncate as specified in the truncation rule section below, then multiply total protein by 1×10^6 (1,000,000).
 - Protein normalized concentration = truncated observed concentration / (10^6 x truncated total protein)

IgG-normalizations for serum samples are performed by dividing VRC07-523LS levels (μ g/mL) by the average reference values for total IgG concentrations in serum in the USA (1165 mg/dL), as following:

- VRC07-523-LS concentration in serum normalized by total IgG (pg VRC07-523LS/ng total IgG):
 - Units: VRC07-523LS units are μ g/mL, and total antibody units are mg/dL. Truncate as specified in the Truncation Rule section below, then divided total antibody by 100.
 - Antibody normalized concentration = truncated observed concentration / (10^{-2} x U.S. reference total antibody)

Truncation rules are applied for SMCxPro, serum, total IgG, and total protein data as following:

- SMCxPro truncation: For results under the smaller value of limit of detection (LLoD) and sample type specific limit of quantification (LLoQ), they are truncated at lower limit of quantification (LLoX) / 2 where LLoX is minimum(LLoQ, LLoD)
- serum truncation: Baseline serum concentrations below the lower limit of quantification (LLoQ = 45.7 ng/ml = 0.0457μ g/ml) are replaced with LLoQ/2. No post-baseline concentrations are below the LLoQ.

- Total IgG truncation: Total IgG (total IgG = Hu IgG1 + Hu IgG2 + Hu IgG3 + Hu IgG4). Any missing subclass will be treated as zero for the purpose of calculating total IgG. If IgG1, IgG2, IgG3, and IgG4 subclasses are all missing for a sample, the sample will be treated as not collected/no sample recovered, and total IgG will be set to NA. Total IgG concentration will be compared to 48 ng/mL; if it is less than 48 ng/mL, the sample will be flagged in the analysis dataset and excluded from the analysis without truncation.
- Total protein truncation: Compared total protein concentration to 0.167 mg/mL, which will be the last curve point and considered as the LLoQ. If concentration < 0.167 mg/mL, then it will be truncated as $0.5 * 0.167$ mg/mL

Body-weight adjustment will be performed by dividing the IgG- and protein-normalized VRC07-523LS levels by the body weight at baseline. Dose-amount adjustment will be performed by dividing the IgG- and protein-normalized VRC07-523LS levels by the body weight at baseline multiplied the dose amount of the products (T1: 10 mg/kg VRC07-523LS, T2: 30 mg/kg VRC07-523LS). The % penetration into different mucosal compartments will be calculated as the protein-normalized VRC07-523LS level in each of the mucosal specimen type divided by that in serum, multiplied by 100.

Pre-treatment participants and all secretion samples deemed hemoglobin-contaminated or unreliable (1. Total IgG concentration < 48 ng/mL, or 2. Total protein concentration < 0.167 mg/mL, with total IgG concentration also < 48 ng/mL) are excluded from the analysis.

Statistical methods

Tabular summaries of the distributions of body-weight-adjusted, IgG- and protein-normalized VRC07-523LS levels, and % penetration of protein-normalized VRC07-523LS is presented by specimen type, treatment arm, sex at birth and visit. Body weight comparisons between treatment arms (T1 vs. T2) and between sexes at birth (Female vs. Male) are presented using the Wilcoxon Rank Sum Test. A table of partial Spearman's rank correlation coefficients of specimen comparison and p-values, adjusted for treatment group (T1 vs. T2) and sex at birth (males vs. females), is presented by visit. P-values are adjusted for multiple comparisons by controlling the false discovery rate (FDR) using the Benjamini-Hochberg procedure [9] and the q-value [10]. Results are significant if the adjusted p-value or q-value ≤ 0.05 .

Comparisons of dose-amount-adjusted, IgG-normalized VRC07-523LS concentrations between visits (v2 vs. v5, v2 vs. v7, v2 vs. v9, v4 vs. v6, v4 vs. v8, v6 vs. v8) are made using the Wilcoxon Signed-Rank test, and comparisons between sexes at birth at visits 4 and 5 are made using the Wilcoxon Rank Sum test. Additionally, comparisons of body-weight-adjusted, IgG-normalized VRC07-523LS concentrations between treatment arms at visits 4 and 5 are made using the Wilcoxon Rank Sum test. Comparisons are made for the % penetration of protein-normalized VRC07-523LS between visits, and specimen types using Wilcoxon Signed-Rank test; and between treatment arms using Wilcoxon Rank Sum test; and between sex at birth, controlling for treatment arms using Van Elteren Test. Comparisons are conducted between levels normalized using actual total protein concentrations and those normalized using the U.S. reference protein concentration (70 g/L) with treatment arms (T1 and T2) pooled using the Wilcoxon Signed Rank Test. Linear mixed-effect regression analyses are performed modeling natural log-transformed concentrations as a function of time since most recent infusion, sex at birth, and treatment group. Linear regressions are performed modeling the difference between natural log-transformed concentrations between visits adjusting for the difference between number of days since last infusion at compared visits, as well as sex at birth and treatment group. P-values are adjusted for multiple comparisons by controlling the false discovery rate (FDR) using the Benjamini-Hochberg procedure [9]

and the q-value [10]. Results are significant if the adjusted p-value or q-value ≤ 0.05 . Comparisons are conducted for groups with at least 3 data points for paired test and at least 5 for unpaired test.

The distributions of body-weight-adjusted IgG- and protein-normalized VRC07-523LS levels, and total IgG over time are displayed graphically by specimen type, assigned sex at birth, and treatment arm. Data points for each participant are connected by a gray solid line. Additionally, the distributions of body-weight-adjusted IgG- and protein-normalized VRC07-523LS levels over time are displayed graphically by treatment arm, with all specimen types plotted together. Data points for each participant are connected by a gray dashed line, while median levels at each timepoint for each specimen type are connected by a colored solid line. The distributions of body-weight-adjusted IgG-normalized VRC07-523LS levels over actual study days since enrollment are displayed graphically by specimen type, assigned sex at birth, and treatment arm. Data points for each participant are connected by the colored dashed line.

Correlations of dose-amount-adjusted, IgG-normalized VRC07-523LS concentrations across specimen types by visits are reported in two ways: (1) sex at birth plotted together but distinguished by shapes, and treatment arms plotted together but distinguished by colors (2) separately for female and male participants, and treatment arms plotted together but distinguished by colors. Correlations of IgG-normalized VRC07-523LS concentrations across specimen types by visits are reported in two ways: (1) separately for treatment arms, and sex at birth plotted together but distinguished by shapes (2) separately for treatment arms, and sex at birth. Correlation of IgG levels and protein levels across specimen types by treatment arms and visits are reported as well. Spearman's rank correlation coefficients and their associated p-values are calculated. Comparisons only done when there are at least 5 data points in each group.

